6.1.2.7 Proportion of children cured at Day 7 follow-up

A child is defined as cured if he/she recovers from illness. A child will be counted in the numerator as cured if his/her status at the time of Day 7 follow-up is at home “well, completely recovered” and the follow-up date is within 7 days of Day 0, considering a + 3 days window (10th day included). The denominator will be all children recruited.

Children for whom no Day7 data are available or withdrew prematurely from the study will be assumed cured by Day7.

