Electronic clinical decision support algorithms (CDSAs) provide an electronic step-by-step guide through a clinical consultation for healthcare providers, supporting the integrated disease management approach promoted by WHO. Recent studies of two such tools, based on IMCI and national guidelines, have demonstrated potential for significant improvements in health outcomes and large reductions in unnecessary antimicrobial prescribing.^{29,30} The use of one such tool by healthcare providers in consultations for all acutely unwell children was found to improve cure rate at day 7 (97% compared to 92% in routine care) whilst reducing antibiotic prescriptions from 84% to 15%.²⁹ Another tool, ePOCT, used for children with fever and integrating point of care diagnostic tests, reduced clinical failure rate to 2% (compared to 5% in routine care) and antibiotic prescriptions to 11% (from 95%).³¹

The mechanisms by which CDSAs impact health worker practice may stem from the fact that the electronic algorithms, by design, provide support in decision making for any combination of clinical findings, whereas paper-based IMCI or national guidelines are, by necessity, reductionist.¹⁰ In a mixed-methods exploration of the reasons for non-adherence to IMCI guidelines by health workers, Lange and colleagues described “cognitive overload” as a contributory factor to non-adherence.³² In such circumstances, support to the complex clinical

decision making process with CDSAs can facilitate health workers to provide higher quality care. This is likely to be particularly true in the case of introducing novel technology such as pulse oximetry, which adds an additional level of complexity to the integrated clinical assessment of children.

Implementing pulse oximetry embedded into a CDSA has the potential to improve the detection of children with severe disease and improve the adherence of healthcare providers to evidence-based, integrated disease management guidelines. We hypothesise that these interventions will result in a reduction in adverse health outcomes through better treatment and referral decisions, and an improvement in quality of care through the rational use of essential medicines and improvements in the health worker and caregiver experience.

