3.1.2 Study procedures

Research assistants (RAs) will screen and recruit participants in the waiting area prior to consultation (Day 0). Following children's caregiver informed consent, the RA will record participant name, contact details, sociodemographic details and reason for attendance prior to consultation. In case of critical and emergency cases, children will be seen immediately by the HCP. The clinical consultation will be conducted by HCPs, who in the post-intervention phase will have been advised to use the devices.

After consultation, the RA will extract information from clinical records, the caregiver and/or medical records and will document them in the database. This information includes final diagnosis, oxygen saturation and results of laboratory investigations, prescribed medication, referral or follow-up advice and usage of pulse oximeter and/or CDSA.

Follow-up at Day 7 will be conducted by phone by an RA. If phone follow-up fails, three attempts will be made on the subsequent three days to reach the caregiver. Community mechanisms to facilitate follow-up (such as arranging a call with a community health worker) will be used, with consent, for caregivers without access to a phone. A structured questionnaire will be administered to assess the primary and secondary outcomes, including details of any government or private hospital admission. In case of non-recovery, if the child is still at home, the study team will advise the family to return to the PHC clinic for a follow-up consultation. Refer to "Participant timeline" section of the Protocol for additional details.

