6.1.1 General definitions

Day 7 assessment

Day 7 assessment refers to information reported by the caregiver after Day 0 and recorded in Day 7 form. Data collected as part of unscheduled visits are also integrated in these forms. If multiple successful follow-up assessments for the same child are recorded within the Day7 database, the most recent follow-up assessment will be used. To limit potential recall bias, assessments conducted far beyond the expected follow-up time will be dropped, i.e. 30 days from Day 0.

Death

A child will be considered deceased if, from Day 7 assessment, his/her status at the time of follow-up is “deceased”. In case of implausible death date (i.e. prior to enrolment date), death will be assumed to be within 7 days of Day0.

Hospitalisation

A child will be considered hospitalised if, from Day 7 assessment, he/she went to a hospital, was admitted overnight or if his/her status at the time of follow-up is “hospitalised”. In case of implausible hospitalisation date (i.e. prior to enrolment date), hospitalisation will be assumed to be within 7 days but after 24hrs of Day0.

Hospitalisation within 24hrs of Day0

For the purpose of primary analysis, a child will be considered admitted to hospital within 24hrs of Day0 consultation if the date of hospitalisation is the same as Day0 date or is one day after Day0 date.

Referral

A child will be considered to be referred (either to a hospital or to an inpatient part of a larger primary healthcare facility) if, at Day0, the research assistant confirms that an urgent referral advice was recorded for the child. If urgency is unknown, referral will be assumed to be urgent.

Antibiotics

Antibiotics will be defined in accordance with the WHO antibiotic point prevalence survey (PPS) methodology [4, 5, 6] and therefore only antibacterials for systemic use will be taken into account.

SpO2 values

SpO₂ should be recorded during the Day0. For the outcomes, the following measures will be taken for spurious and missing SpO₂ values:

- If SpO₂ value is not available, the child will be assumed normoxaemic
- If $70 \leq \text{SpO}_2 < 90\%$, the child will be assumed (with accuracy) to have severe hypoxaemia
- If $40 \leq \text{SpO}_2 < 70\%$, the child will be assumed (with low accuracy) to have severe hypoxaemia
- If $\text{SpO}_2 < 40\%$, the value will be considered spurious (e.g. due to incorrect dataentry) and treated as not available, i.e. the child will be assumed normoxaemic.

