6.1.2 Health, hospitalisation and referral outcomes

6.1.2.1 Proportion of children with a severe complication by Day 7

Severe complication is defined as death or secondary hospitalisation. Secondary hospitalisation refers to any delayed hospitalisation (occurring at any point greater than 24hrs after the Day 0 consultation) and any hospitalisation occurring without a referral. Information on death and hospitalisation will be taken from Day7 follow-up assessment.

Death will be counted in the numerator if death date is within 7 days of Day0 (7th day included). Hospitalisation will be counted in the numerator if the child was not referred at Day0 or hospital admission date is within 7 days of Day0 (7th day included) but after 24hrs of Day0.

The denominator will be all children recruited. Children for whom no death and hospitalisation data are available or withdrew prematurely from the study will be assumed to be alive and not hospitalised by Day7.

6.1.2.2 Proportion of children admitted to hospital within 24 hours of Day 0 consultation and as a result of a referral

Information on hospitalisation will be taken from Day7 follow-up assessment.

Hospitalisation will be counted in the numerator only if the child received a referral advice (as per definition above) at Day0 and hospital admission date is within the end of the following day. The denominator will be all children recruited.

Additionally, the proportion will be calculated and reported using only children who were referred as denominator.

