6.1.2.5 Proportion of children who completed referral as reported at Day 7 follow-up

A referral will be considered completed if a child attended a hospital, whether he/she was admitted or not. Children will be counted in the numerator if they received a referral advice (as per definition above) and their caregiver reported to have sought care in a hospital and the follow-up date is within 7 days of Day 0, considering a + 3 days window (10th day included). The denominator will be all children recruited.

Additionally, the proportion will be calculated and reported using only children who were referred as denominator.

Children for whom no Day7 data are available or withdrew prematurely from the study will be assumed not attending a hospital by Day7.

6.1.2.6 Proportion of children with non-severe disease referred to a higher level of care on Day 0

Children with non-severe disease who received a referral advice (as per definition above) at Day0 will be counted in the numerator. The denominator will be all children recruited. Non-severe disease will be defined in a separate document.

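### Cure at Day 7: read literally, the SAP counts a recovered child last reached on days 11–30 as not cured, but a child never reached as cured

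*SAP*

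**What the plan says.** Two parts of the SAP have to be read together.

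- **SAP 6.1.1 (Day 7 assessment)** decides which contact represents the child. If several succeeded, "the most recent follow-up assessment will be used". Only very late ones are removed: "assessments conducted far beyond the expected follow-up time will be dropped, i.e. 30 days from Day 0". Contacts on days 11–30 therefore remain Day 7 data.
- **SAP 6.1.2.7 (cure)** requires full recovery at that contact and that "the follow-up date is within 7 days of Day 0, considering a + 3 days window (10th day included"). The denominator is all recruited children. Then: "Children for whom no Day7 data are available or withdrew prematurely from the study will be assumed cured by Day7".

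Calls are planned for a short window. SAP 3.1.2 says that if the Day 7 call fails, "three attempts will be made on the subsequent three days to reach the caregiver", and Protocol 7.1.1 sets the window as Day 7 to Day 10.

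Cure is one of four secondary outcomes. SAP 6.3 describes missing data by period and SAP 5.4 gives Day 7 follow-up counts by period; neither mentions contact timing. In SAP 6.2.4 the sensitivity analyses for secondary outcomes cover hospitalisation only.

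**The concern.** Two groups of children lack a usable status by day 10, and the rule gives them opposite values. Those last reached on days 11–30 have Day 7 data, fail the date test and count as not cured, whatever the caregiver reported. Those never reached, or reached only after day 30 and so dropped, count as cured. Additional information can only worsen the recorded outcome: a child reported well on day 7 and again on day 15 is judged on the day-15 call and becomes not cured.

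The 30-day allowance suits outcomes decided by the date of an event. For severe complications, "Death will be counted in the numerator if death date is within 7 days of Day0", so a late call can still establish what happened by day 7. Cure is the status at the contact itself, so a late call cannot do this. Completed referral (SAP 6.1.2.5) uses the same day-10 test, but children without data "will be assumed not attending a hospital by Day7", so late and never-reached children get the same value. Among the secondary outcomes, the opposite treatment is specific to cure.

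At stake is the pre/post comparison of cure. If follow-up timeliness differed between periods, the comparison would partly reflect call logistics.

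**Working it through.** **Step 1. Apply the rules literally to a child who has recovered.**

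| Contacts | Assessment used (6.1.1) | Cure value (6.1.2.7) |
|---|---|---|
| Day 7 only | day 7 | cured |
| Day 7 and day 15 | day 15 | not cured |
| Day 12 only | day 12 | not cured |
| After day 30 only | none (dropped) | assumed cured |
| Never reached | none | assumed cured |

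**Step 2. Inputs for size.** The plan has no figure to reproduce here: it gives no expected cure rate, late-contact rate or intra-cluster correlation for cure. Assumptions:

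- True cure c = 0.92 or 0.97. Protocol 3.2 cites a study of another tool that was found to "improve cure rate at day 7 (97% compared to 92% in routine care"). The same c is applied to every contact group and both periods.
- Never reached u = 0.05 in both periods.
- Last reached on days 11–30: l, varied from 0 to 0.03.

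**Step 3. Formulas.**

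- Literal reading: reported cure = c(1 − u − l) + u. The slope is −c per unit of l.
- Milder reading (no Day 7 data means none by day 10): reported cure = c(1 − u − l) + u + l. The slope is +(1 − c).

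The two differ by exactly l.

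**Step 4. Results for c = 0.92, u = 0.05.**

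| l | Literal | Milder |
|---|---|---|
| 0 | 92.40% | 92.40% |
| 0.01 | 91.48% | 92.48% |
| 0.02 | 90.56% | 92.56% |
| 0.03 | 89.64% | 92.64% |

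For example, at l = 0.02: 0.92 × 0.93 + 0.05 = 0.9056 (literal) and 0.92 × 0.93 + 0.07 = 0.9256 (milder).

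With no true change in cure, the literal rule gives these apparent differences:

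- late contact 2% to 1%: +0.92 points
- 3% to 1%: +1.84 points
- 1% to 2%: −0.92 points
- unchanged: 0, although cure is lowered in both periods

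Under the milder reading, 3% to 1% gives −0.16 points. With c = 0.97 the literal slope is 0.97 points per point (96.18% at l = 0.01, 95.21% at l = 0.02).

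These figures move children between in-window and late contact. If one point of children moves from never reached to late instead, literal cure falls by exactly one point, because u falls by 0.01 while 1 − u − l is unchanged.

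**The case against.** The strongest reply is that no Day 7 data was meant as none by day 10. SAP 6.3 lists children not reached at Day 7 beside those lost to follow-up as the main source of missing values, and the plan defines Day 7 with a three-day window. On that reading the asymmetry disappears and the residual effect is 0.08 points per point. The reply has some weight but does not settle the matter. The operative best-case sentence in SAP 6.3 names only children lost or withdrawn, SAP 6.1.1 keeps contacts to day 30 as the Day 7 assessment, and SAP 6.1.2.7 applies its date test separately. Two competent analysts could report cure rates that differ by the whole late-contact rate.

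The second reply is that late contacts may be rare, since calls are planned only for days 7–10. This stands as a limit on size. The 30-day and multiple-assessment rules show that the authors provided for such contacts, but the documents do not say how many there are.

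A reader might infer that the cure comparison is biased, or biased in favour of the intervention. The documents do not support this: bias needs a change in late contact between periods, and neither its existence nor its direction is given. Nor do they support treating a cure gain like the 5 points cited in Protocol 3.2 as a likely artefact. Under the literal rule that would need late contact to fall by about 5/0.92 = 5.4 points, and the trial sets no target difference for cure.

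**Conclusion.** The literal rule is wrong as written for one secondary outcome: it scores late-reached and never-reached children in opposite ways, and no planned analysis would reveal this. A change in late contact between periods would appear as a change in cure of about 0.92 points per point at 92% true cure (0.97 at 97%), in the opposite direction. This assumes equal true cure in all contact groups and a constant never-reached share. Under the milder reading the effect is 0.08 points per point (at 92% true cure), with the sign reversed.

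Confidence is high for what the text literally does, and at most medium that the effect is material, because the late-contact rate is not given. Both primary outcomes are recorded on Day 0 and are untouched. The point should be fixed before analysis, but it does not threaten the trial's main comparison.

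**What to change.** 1. In SAP 6.1.2.7, apply the most-recent rule only among assessments dated no later than day 10. A later call then cannot override an in-window report, and an earlier contact (for instance an unscheduled sick visit merged into the Day 7 form) cannot override the last report by day 10. Make the same choice of assessment for completed referral in 6.1.2.5.
2. State that a child with no assessment by day 10, whether reached late or never, is handled in one way, under the SAP's existing missing-data rule. The all-recruited denominator and best-case assumption can stay as the planned analysis; the remaining sensitivity to timing is then the 0.08 points per point shown above.
3. Tabulate contact timing by period: by day 10, days 11–30, after day 30, never.
4. As a sensitivity analysis only, report cure among children assessed by day 10 and a worst-case bound beside the planned figure. In the illustration (c = 0.92, u = 0.05, l = 0.02) these are 92.0% among those assessed, 0.92 × 0.93 = 85.56% worst case, and 85.56 + 7 = 92.56% best case.

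The cost is a few sentences of SAP wording and one small table. No new data are needed, because 6.1.2.7 already requires the follow-up dates.

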6.1.3 Antibiotic-related outcomes

6.1.3.1 Proportion of children prescribed an antibiotic at Day 0

Information on antibiotics prescription are recorded by the RA on Day 0, after the clinical consultation. The data collection tool is structured in a way to facilitate the reporting of antibiotics, starting with single-drug questions for the most common/important ones to drop-down lists for other antibiotics/treatments and free text. All options will contribute to determine whether an antibiotic prescription was given. A child will be considered prescribed with an antibiotic if:

- ξ “Yes” was selected for at least one single-drug question
- ξ “No” was selected for all single-drug questions but one or more antibiotics were selected from the antibiotics/treatments drop-down list
- ξ “No” was selected for all single-drug questions, antibiotics were not selected from the other antibiotics/treatments drop-down list but antibiotics were listed in the free text field (conditional to feasibility of assessing free text)

All children recruited will be counted in the denominator.

6.1.3.2 Proportion of children prescribed a diagnosis-appropriate antibiotic

Appropriateness of antibiotic prescription in relation to diagnosis will be evaluated as:

- ξ Proportion of children who received a diagnosis for which a systemic antibiotic was indicated and a systemic antibiotic was prescribed
- ξ Proportion of children who received a diagnosis for which a systemic antibiotic was not indicated and systemic antibiotic was prescribed
- ξ Proportion of children who received first-line (or second-line) antibiotics according to recommendations for IMCI diagnoses for which specific antibiotic(s) are indicated

Only children with a diagnosis for which a systemic antibiotic was indicated will be counted in the denominator for the first proportion, only children with a diagnosis for which a systemic antibiotic was not indicated will be counted in the denominator of the second proportion, and only children who received an IMCI diagnosis requiring specific antibiotics will be counted in the denominator of the third proportion.

Diagnoses will be classified according to whether systemic antibiotics are indicated, based on IMCI and other relevant national guidelines as used for the CDSA, using the structured data entry and free text if feasible. Diagnosis classification will be defined in a separate document.

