7.1.2 Routine data

CDSA individual consultation data

Routine individual consultation data will be recorded in the CDSA in all intervention facilities in the post-intervention period. As part of the intervention, healthcare providers will be asked to use MedAL-R during their consultations. When they do so, they will routinely enter all data necessary for the clinical management of children 0 – 59 months of age into MedAL-R. Data used within TIMCI will cover clinical presentation (including symptoms and dangers signs), medical history (including HIV and TB status if known), all physical exams and measurements relevant for clinical assessment (including pulse oximetry), and laboratory investigations. Automated recommendations from CDSA on diagnosis and child management will also be collected, as well as healthcare provider's agreement or disagreement with these recommendations and possible additional diagnoses and treatments, which will be manually entered. A description of the variables extracted from CDSA is available in the appendix.

HMIS aggregate facility data

HMIS data will include the total number of outpatient consultations – for all patients and for children 0 – 59 months of age (disaggregated by new and follow-up visit if possible) –, disease burden, and any other relevant indicators if available (such as referral rate or mortality rate), disaggregated by age and sex if routinely collected with this granularity.

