9.1.1 Regulatory status of the intervention

Pulse oximetry

The pulse oximetry device selected for the TIMCI project is the Acare AH-MX device. This was selected as it is available through the UNICEF catalogue, which infers a level of quality and device appropriateness. The competitive procurement process established by UNICEF incorporates pulse oximetry specifications developed through a collaborative process involving global and national level experts. Devices in the catalogue have regulatory approval from a stringent regulatory authority (SRA) such as the United States Food and Drug Administration (US FDA) or Conformité Européenne (CE) mark.

Country level regulatory approval will vary. It is possible that the devices will have approval in some of the countries. If the device does not have pre-existing regulatory approval in a project country, the project team will work with the MOH to receive a waiver to use the device for the study purposes. If appropriate, the study team will continue to work with the manufacturer and MOH in each country to receive a permanent regulatory approval to facilitate scale of that device.

Clinical Decision Support Algorithm

The regulatory classification of clinical decision support software is currently subject to debate at the US FDA, depending on how and in what context the software is used. In this study, the CDSA is intended to provide decision support for the diagnosis and treatment of childhood illness. It will collate and analyse patient-specific information to suggest possible diagnoses and recommend treatment plans or diagnostic tests to healthcare providers (HCPs). These suggestions and recommendations will be evidence-based and will support the decision-making of the HCP when considering treatment options or diagnostic tests for a patient. The HCP may then use this information to make a decision about the care of the patient, along with other information and factors of which he/she is aware. In addition, the CDSA presents a low risk profile since it will support the implementation of and strengthen the adherence to standard clinical guidelines. These functions do not meet the definition of a medical device per country regulatory authorities and the CDSA is therefore regarded as a non-regulated device.

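### SAP 6.1.3.2 puts a child with one antibiotic-indicated and one non-indicated diagnosis in both appropriateness groups, so correct treatment of that child also counts as prescribing without indication

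*SAP*

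**What the plan says.** The section opens with "Appropriateness of antibiotic prescription in relation to diagnosis will be evaluated as" and lists three proportions. The first is the share prescribed a systemic antibiotic among children with an indicated diagnosis. The second is "Proportion of children who received a diagnosis for which a systemic antibiotic was not indicated and systemic antibiotic was prescribed". The third concerns first- or second-line choice for IMCI diagnoses that call for specific antibiotics.

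The denominators are then fixed. For the first: "Only children with a diagnosis for which a systemic antibiotic was indicated will be counted in the denominator for the first proportion". For the second: "only children with a diagnosis for which a systemic antibiotic was not indicated will be counted in the denominator of the second proportion".

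The unit being classified is the diagnosis: "Diagnoses will be classified according to whether systemic antibiotics are indicated". What is deferred is that same classification: "Diagnosis classification will be defined in a separate document". Neither document gives a hierarchy or a child-level rule for a child whose recorded diagnoses fall on both sides.

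Protocol 6.4.1 and SAP 3.1.4 list this item among the other outcomes of interest, not the primary or secondary ones. Under SAP 6.2.1, other binary outcomes are compared between periods with the same random-effects logistic model as the primary outcomes, giving odds ratios and risk differences.

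**The concern.** Both groups are defined by the presence of one qualifying diagnosis, so they overlap. A child with one diagnosis of each kind belongs to both. If the antibiotic is given as the indicated diagnosis calls for, the first proportion scores a success and the second scores a prescription without indication. Because the three proportions are introduced as measures of appropriateness, readers will take the second as inappropriate prescribing.

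Two things are at stake. The level of the second proportion is wrong whenever such children exist. The pre-post contrast is also exposed, because it depends on how often a second, non-indicated diagnosis is written down for children who have an indicated one. The primary antibiotic outcome counts any systemic antibiotic, so it cannot separate removal of unneeded prescribing from withholding of needed treatment. The proportions in 6.1.3.2 are where the plan looks at that distinction.

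**Working it through.** The plan states no expected value for this outcome, so there is no figure to reproduce. The check applies the written definition algebraically.

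**Inputs**

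- I, share of children with at least one indicated diagnosis: not in the documents; assumed 30%, range 20–40%.
- a, share of those children prescribed a systemic antibiotic: not in the documents; assumed 95% (100% for perfect prescribing).
- b, share prescribed among children with no indicated diagnosis: not in the documents; derived below from the 60% pre-intervention antibiotic prescription assumed in Protocol 6.6.1 and SAP 3.4.
- m, share of indicated children who also have a non-indicated diagnosis recorded: not in the documents; assumed 20% and 60%.

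Two simplifications: prescribing in indicated children does not depend on whether a second diagnosis is recorded, and every child with no indicated diagnosis has at least one diagnosis classed as non-indicated.

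**Formula.** As written, the second proportion is P2 = (I·m·a + (1−I)·b) / (I·m + (1−I)). Restricted to children with no indicated diagnosis, it is b. The excess is P2 − b = I·m·(a−b) / (I·m + 1−I). It is zero if m = 0, and it rises with m only when a > b.

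**Perfect prescribing** (a = 100%, b = 0%, I = 30%). The right answer is 0%. The written rule gives 0.06/0.76 = 7.9% at m = 20% and 0.18/0.88 = 20.5% at m = 60%.

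**Calibration to 60% overall prescribing.** I·a + (1−I)·b = 0.60, so at I = 30%, b = (0.60 − 0.285)/0.70 = 45.0%.

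**Identical prescribing, co-recording rising from 20% to 60%**

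| I | b | P2 at m = 20% | P2 at m = 60% | Change |
|---|---|---|---|---|
| 20% | 0.41/0.80 = 51.3% | 0.448/0.84 = 53.3% | 0.524/0.92 = 57.0% | +3.6 points |
| 30% | 0.315/0.70 = 45.0% | 0.372/0.76 = 48.9% | 0.486/0.88 = 55.2% | +6.3 points |
| 40% | 0.22/0.60 = 36.7% | 0.296/0.68 = 43.5% | 0.448/0.84 = 53.3% | +9.8 points |

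At I = 30% the spurious odds ratio is (0.552/0.448)/(0.489/0.511) ≈ 1.29. The child-level definition gives no change in any row.

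**A real improvement.** Take I = 30%, a = 95% and a true fall in b from 50% to 30%. With m constant at 20%, P2 goes from 0.407/0.76 = 53.6% to 0.267/0.76 = 35.1%, an apparent fall of 18.4 points in place of 20. If m also rises to 60%, it goes from 53.6% to 0.381/0.88 = 43.3%, an apparent fall of 10.3 points.

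**The case against.** The strongest reply concerns reach. This is one of three proportions under an outcome outside the primary and secondary lists. A child with mixed diagnoses is counted correctly in the first proportion, and the third is untouched. The primary antibiotic outcome (SAP 6.1.3.1) covers all recruited children and is not affected. All of that stands.

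The mechanism for a shift between periods is also inferred. Protocol 9.1.1 says of the decision support tool that "It will collate and analyse patient-specific information to suggest possible diagnoses", and Protocol 7.1.2 refers to "possible additional diagnoses and treatments, which will be manually entered". The second of these describes routine consultation data. For the pre-post study, research assistants extract the diagnosis from clinical records in both periods (Protocol 6.5.1, SAP 3.1.2). Protocol 7.1.1 plans linkage to the tool's data after introduction and Tab. 4 lists a diagnosis form drawn from it, so a route exists, but SAP 6.1.3.2 does not say that those diagnoses feed this outcome. A reader might infer that introducing the tool will bias the comparison. The documents do not support that: they give no co-recording rates and do not say that the rates will rise.

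A reader might also infer that any extra diagnosis worsens the result. It does not. Two diagnoses of the same kind misplace no one, and further non-indicated diagnoses in children who have no indicated one change nothing. The direction also needs prescribing to be more frequent in indicated children than in the rest, which is expected but assumed. Where it holds, a rise in co-recording would make the intervention look worse, not better.

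Finally, the separate classification document was not available, and a rule for mixed diagnoses could sit there. The SAP, however, promises only a classification of diagnoses in it. The denominators are set in the SAP itself, and a complete list of diagnoses would leave the overlap in place. The malaria outcomes that follow (SAP 6.1.4.2 to 6.1.4.4) use positive, negative and untested groups that do not overlap.

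**Conclusion.** The definition is faulty as written, and the point is of moderate importance. That the groups overlap, and that the second proportion cannot reach 0% under correct prescribing once any child has one diagnosis of each kind, follows from the text and needs no assumption about change over time. Its size is illustrative: 7.9% in place of 0% at a 30% indicated share and 20% co-recording.

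Bias in the pre-post comparison is conditional. It requires co-recording to change and a > b. If co-recording rose from 20% to 60%, the second proportion would rise by about 6.3 points with identical prescribing, or 3.6 to 9.8 points for an indicated share of 20–40%. Those figures rest on assumed values of I, a and m, with only the 60% overall prescribing taken from the plan. A smaller rise gives a smaller shift, and no rise gives no spurious change, although a true change in b is still somewhat diluted. No conclusion about the primary outcomes or the sample size is affected.

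**What to change.** Amend SAP 6.1.3.2 so that the first two groups are mutually exclusive at child level:

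- Group 1: children with at least one diagnosis for which a systemic antibiotic is indicated.
- Group 2: children with no such diagnosis.

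Compute the first proportion in group 1 and the second in group 2 only; leave the third as it is. State this rule in the SAP itself and keep the separate document for the list of diagnoses. Report the number of diagnoses per child by period, so that any change in recording is visible beside the result.

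The cost is a sentence or two of SAP text and one derivation rule. No new data are needed, and no clinical rule changes.
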